**SIGNATURE PAGE FOR VANDA PHARMACEUTICALS INC.**

**Amendment No. 6 to VP-VLY-686-3301**

Approved by the following:

Program Lead:

*[name]*

12/12/2022 | 5:04 PM EST

\_\_\_\_\_  
[name]

\_\_\_\_\_  
Date

Senior Vice President, Research &  
Development Committee

Medical Director:

*[name]*

12/12/2022 | 5:02 PM EST

\_\_\_\_\_  
[name].

\_\_\_\_\_  
Date

Medical Director

Name of Sponsor/Company: Vanda Pharmaceuticals Inc.	
Name of Investigational Product: Tradipitant (VLY-686)	
Name of Active Ingredient: {2-[1-(3,5-Bistrifluoromethylbenzyl)-5-pyridin-4-yl-1H-[1,2,3]triazol-4-yl]-pyridin-3-yl}-(2-chlorophenyl)-methanone	
Title of Study: A Multicenter, Randomized, Double-Blind, Placebo-Controlled Phase III Study to Assess the Efficacy of Tradipitant in Relieving Symptoms of Gastroparesis	
Study center(s): Approximately 50 centers in the United States	
Indication: Diabetic & Idiopathic Gastroparesis	Phase of development: III
Number of subjects (planned): Up to 800 subjects will enroll in the study. Group 1: Approximately 200 gastroparesis subjects will be determined eligible to enter the Evaluation Phase and be randomized to one of 2 arms (100 per arm, 1:1 randomization scheme). Group 2: Up to 600 gastroparesis subjects that are not eligible to be randomized will enter into the 12 week Open Label Phase of the study.	
Inclusion Criteria: 
 
1. Male and female subjects aged 18 – 70 years (inclusive);
 
2. Diagnosed with gastroparesis: 
 
a. Demonstrated delayed gastric emptying of a solid meal via either scintigraphy, gastric breath test, or wireless motility capsule within 10 years of screening. If solid meal is not tolerated, a liquid meal may be used instead to demonstrate delayed gastric emptying via scintigraphy
 
b. Presence of nausea symptom for at least 6 months prior to screening
 
 
 
3. Patient’s gastroparesis symptoms persist despite diet and/or life-style modifications;
 
4. Body Mass Index (BMI) of <math>\geq 18</math> and <math>< 40 \text{ kg/m}^2</math> (BMI = weight (kg)/ [height (m)]);
 
5. Subjects must agree to the following study restrictions: 
 
a. Males of procreative capacity (not surgically sterile) will use an acceptable method of contraception from randomization through 1 month following the last dose of study medication. Examples of acceptable contraception for males include abstinence, use of a barrier method, or sterilized or post-menopausal partner;
 
b. Females of child-bearing potential (not surgically sterile or post-menopausal, defined as 12 months without menses) will use an acceptable method of contraception from 1 month prior to randomization (or screening, if earlier) through 1 month following the last dose of study medication. Examples of acceptable methods of contraception for females include abstinence, double barrier method, IUD, hormonal contraception, or sterilized partner;
 
 
 
	

6. Ability and acceptance to provide written informed consent;
7. Willing to participate in the pharmacogenomics sample collection;
8. Willing and able to comply with all study requirements and restrictions, including but not limited to:
  - a. Daily symptom diary completion,
  - a. Prohibited medications,
  - b. Strict control of blood glucose (T1DM and T2DM patients);
9. Willing to not participate in any other interventional trial for the duration of their participation.

**NOTE: ADDITIONAL CRITERIA ARE CONFIDENTIAL AND SHOULD NOT BE SHARED WITH SUBJECTS, POTENTIAL SUBJECTS, OR ANYONE OUTSIDE OF THE IMMEDIATE STUDY TEAM.**

**Additional Inclusion Criteria for Group 1/Evaluation Phase:**

10. Diagnosed with idiopathic or diabetic gastroparesis with moderate to severe nausea:
  - a. At least 24 screening diary entries,
  - b. PAGA-SYM individual nausea score  $\geq 2$  at Visit 1, and
  - c. Average daily diary nausea severity  $\geq 2.5$  during the screening period,
  - d. At least one episode of vomiting during the screening period.

**Additional Inclusion Criteria for Group 2/Open Label Phase:**

11. Diagnosed with diabetic, idiopathic, post-surgical or viral gastroparesis,
  - a. Presence of nausea (PAGA-SYM individual nausea score  $\geq 1$  at Visit 1),
  - b. At least 24 screening diary entries,
  - c. Patients who do not qualify for Group 1/Evaluation Phase.

**Exclusion Criteria:**

1. Another active disorder or treatment which could explain or contribute to symptoms in the opinion of the Investigator (including but not limited to gastric malignancy, neurological disorder, or heavy doses of strong anticholinergics);
2. Gastric or parenteral feeding within 4 weeks of screening for Group 1;
3. Pregnancy or nursing;
4. History of intolerance and/or hypersensitivity to medications similar to tradipitant and its accompanying excipients;
5. History (including family history) or current evidence of congenital long QT syndrome or known acquired QT interval prolongation (including QTcF  $> 450$  in males or  $> 470$  in females at screening);

6. History of suicide attempt and/or suicidal ideation (of type 4 or 5 on the Columbia Suicide Severity Rating Scale (C-SSRS)) within 2 years of screening or subject is at risk of suicide at Screening or Baseline visits, in the opinion of the investigator;
7. History of an eating disorder within 2 years of screening for Group 1 only and within 3 months of screening for Group 2;
8. Recent history (within six months of screening) of Alcohol Use Disorder or Substance Use Disorder as defined in DSM-5 or evidence of such abuse which may include a positive drug screen at the Screening visit and does not include medical marijuana for Group 2 subjects only
9. Uncontrolled thyroid disease;
10. Unstable cardiac, respiratory, hepatic or renal disease;
11. Indication of impaired liver function (including values for AST, ALT, or bilirubin > 2 times the Upper Limit of Normal, unless isolated bilirubin > 2 x ULN due solely to Gilbert's syndrome) at screening;
12. Has a creatinine level > 2x ULN at screening;
13. Anyone affiliated with the site or sponsor and/or anyone who may consent under duress;
14. Any other reason as determined by the Investigator which may lead to an unfavorable risk-benefit of study participation, may interfere with study compliance, or may confound study results;
15. Evidence of uncontrolled blood glucose (including HbA1C >9 for Group 1 or HbA1C > 11 for Group 2 at screening or metabolic crisis in past 60 days);
16. Surgeries to the stomach including gastrectomy, fundoplication, vagotomy, pyloroplasty, bariatric surgery excluded in Group 1 and excluded in Group 2 if performed < 2 months from screening . Additionally, gastric stimulation device surgically implanted within the last year or if implanted more than a year ago for Group 1 subjects or withing the last 2 months for Group 2 subjects, or have changed stimulation settings within the last 3 months (ie gastric stimulation device must have a stable setting for at least 3 months) for Group 1 and withing the last 1 month for Group 2 subjects
17. Use of prohibited medication or medication with anti-nausea, antiemetic, neuromodulating, or prokinetic effect within 2 weeks of the screening visit EXCEPT when administered on a stable daily dosing schedule (stable for at least 3 months prior to the screening visit) or administered under protocol-specified rescue medication guidelines;
18. Use of the following within 2 weeks of screening: another NK-1 antagonist or a second generation 5-HT3 antagonist for Group 1 and Group 2, phenergan more than 2 times per day for Group 1 only, or opioids more than 2 times per week for Group 1 only;
19. Pyloric injection of neurotoxins (e.g. botulinum type A or B) within 3 months of the Screening Visit for Group 1 or within 1 month of Screening for Group 2;
20. Exposure to any investigational medication, including placebo, within 60 days of the Baseline Visit;

21. Patients who previously participated in study VP-VLY-686-2301 or any other clinical study of tradipitant in the past.

Investigational product, dosage and mode of administration:
 
Group 1: Oral 85 mg tradipitant and matching placebo capsules will be administered. Subjects will be randomized to one of two treatment arms to receive 85 mg tradipitant BID or placebo.
 
Group 2: Open label Oral 85 mg tradipitant capsules will be administered to all group 2 patients.
 
All subjects will be instructed to take 1 capsule in the morning and another approximately 12 hours later in the evening.

Duration of treatment: Up to 12 weeks


Objectives:
 
Primary:
 

• To evaluate the efficacy of tradipitant relative to placebo in change from baseline to Week 12 in the daily nausea severity scores.

 
Secondary:
 

• To evaluate the efficacy of tradipitant relative to placebo in change from baseline in number of days at “0” nausea.

• To evaluate the efficacy of tradipitant relative to placebo in change from baseline of other individual symptoms associated with gastroparesis.

• To evaluate the efficacy of tradipitant relative to placebo in change from baseline of the overall symptom burden associated with gastroparesis.

• To evaluate the efficacy of tradipitant relative to placebo in change from baseline of global improvement and quality of life measures.

• To explore the safety and tolerability of multiple oral doses of tradipitant.


Overall Design:
 
This is a multicenter, randomized, double-blind, placebo-controlled study to be conducted in the United States. Up to eight hundred (800) subjects diagnosed with gastroparesis, who satisfy the selection criteria for the study, will be eligible for one of two groups. Group 1 will enter the Evaluation Phase of the study and Group 2 will enter the Open Label phase of the study. Patients eligible for Group 1 will be randomized to one of two treatment groups. Randomization will be stratified by disease etiology (idiopathic or diabetic), and enrollment for either of the etiologies will be capped at 60% of the total sample size. Patients eligible for Group 2 will enter the Open Label Phase of the study.
 
The study includes two phases: the screening phase and the evaluation phase. The screening phase includes a screening visit to evaluate subjects’ preliminary eligibility for the study. During the screening phase, subjects will collect diary data for at least 4 weeks. The data collected during the screening phase must be reviewed in order to determine eligibility for enrollment into the evaluation phase. Data review will be performed prior or at Visit 2. Patients who to meet all Group 1 eligibility criteria will randomized onto double blind treatment in the evaluation phase. Patients who meet Group 2 criteria or do not meet symptom criteria for randomization but still meet all other eligibility criteria, will be offered open label treatment in the open label arm of the evaluation phase. When enrollment goal is reached for

group 1, group 1 enrollment will be closed and all subsequent patients in screening will be evaluated for group 2 eligibility only.

The Evaluation Phase includes 12 weeks of double blind randomized treatment of placebo or tradipitant (85mg bid, approximately 12 hours apart) for Group 1 or open label tradipitant (85mg bid, approximately 12 hours apart) for Group 2. Daily diaries will be completed during all phases. Clinical evaluations and safety assessments will occur at Screening, Baseline, Week 2, Week 4, Week 6, Week 8, Week 10, and Week 12.

Following the End of Study Visit (Visit 8) patients can opt-in to a one-day optional pharmacokinetic (PK) study where one additional dose of tradipitant will be taken and blood will be drawn pre-dose and, 1, 2, 4, 6, 8-hour post dose to assess drug levels. This optional PK Visit can occur 1-14 days after Visit 8.

**Primary Endpoint:**

Change from baseline to Week 12 in daily individual nausea severity scores (0=none, 1=very mild, 2=mild, 3=moderate, 4=severe, 5=very severe)

**Criteria for evaluation:**

Efficacy:

Efficacy assessments will include:

- Gastroparesis Core Symptom Daily Diary (GCSDD)
- Patient Assessment of GI Disorders – Symptoms Severity Index (PAGI-SYM)
- Global Assessment of Gastroparesis
- Patient Rated Change in Gastroparesis Symptoms
- Patient Global Impression – Change (PGI-C)
- Patient Assessment of Gastrointestinal Disorders – Quality of Life (PAGI-QOL)
- Gastroparesis Treatment Benefit Survey (GTBS)
- Clinician Global Impression – Severity (CGI-S)

Safety:

- Safety and tolerability assessments will include the recording of adverse events (AEs), physical examinations, clinical laboratory evaluations, vital signs, and electrocardiograms.
- The Columbia-Suicide Severity Scale (C-SSRS) will be used to assess suicidal behavior and ideation.

**Sample Size Discussion:**

Based on a two-sided t-test with the 5% significance level, the planned sample size of 100 subjects per arm provides 95% power to detect a mean difference of 0.65 point in the average of daily nausea severity assuming the standard deviation of 1.25 in each treatment group.

11. STATISTICS

11.1. Sample Size and Accrual

Based on a two-sided t-test with the 5% significance level, the planned sample size of 100 subjects per arm (a total of 200 subjects) provides approximately 98% power to detect a mean difference of 0.65 point in the average of nausea severity score assuming the standard deviation of 1.15 in each treatment group. Assuming an equal enrollment for each of diabetic and idiopathic etiology groups, a total of 100 subjects (50 per arm) per etiology will also provide approximately 80% power for each of these groups.

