11.5. Subgroup Analysis

The subgroup analysis (such as, gender, age, etiology, baseline illness severity etc.) for efficacy variables and safety variables may be conducted as described in the SAP.

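### The synopsis and Section 11.1 size the same comparison with different standard deviations (1.25 and 1.15), and the 80% per-etiology power holds only under the smaller one

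*SAP*

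**What the plan says.** The Sample Size Discussion in the protocol synopsis says that 100 subjects per arm, tested with a two-sided t-test at the 5% level, give "95% power to detect a mean difference of 0.65 point in the average of daily nausea severity assuming the standard deviation of 1.25".

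Section 11.1 of the SAP keeps the test, the significance level, the 100 per arm and the 0.65-point difference, but states "approximately 98% power to detect a mean difference of 0.65 point in the average of nausea severity score assuming the standard deviation of 1.15". It then turns to the two etiologies and sets out the condition and the numbers: "Assuming an equal enrollment for each of diabetic and idiopathic etiology groups, a total of 100 subjects (50 per arm) per etiology". The claim made for those numbers is that they "will also provide approximately 80% power for each of these groups".

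Two other places bear on the per-etiology figure. The Overall Design part of the synopsis stratifies randomization by etiology and says that "enrollment for either of the etiologies will be capped at 60% of the total sample size". Section 11.5 says that subgroup analyses, with etiology among the examples, "for efficacy variables and safety variables may be conducted as described in the SAP".

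**The concern.** The SD is one of the few inputs to the sample size, and two values are given for one comparison. Neither is presented as a sensitivity case, and neither place refers to the other. A reader cannot tell which variability assumption, and so which stated power, the trial rests on.

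The choice also decides whether another sentence is true. The per-etiology power follows directly on the SD of 1.15. If 1.25 is the real planning value, that sentence overstates the power. Etiology is the stratification factor and its enrollment is capped, so a reader is likely to take the per-etiology figure seriously.

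**Working it through.** **Inputs**

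| Input | Synopsis, Sample Size Discussion | SAP, Section 11.1 |
|---|---|---|
| Test | two-sided t-test, 5% | two-sided t-test, 5% |
| Subjects per arm | 100 | 100 |
| Difference | 0.65 | 0.65 |
| SD | 1.25 | 1.15 |
| Stated power | 95% | about 98% |
| Per-etiology power | none stated | about 80% at 50 per arm, if enrollment is equal |

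Section 11.1 gives no separate difference for the etiologies, so 0.65 is assumed to apply there too.

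**Formula.** For n per arm, the noncentrality parameter is λ = 0.65 / (SD × √(2/n)), with 2n − 2 degrees of freedom. Power is the probability that a noncentral t variable with these parameters falls outside ± the two-sided 5% critical value.

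**Step 1: reproduce the overall figures (n = 100, 198 df, critical value 1.972).**
- SD 1.15: λ = 0.65 / (1.15 × 0.1414) = 3.997, power 97.8%. This matches the 98% in Section 11.1.
- SD 1.25: λ = 0.65 / (1.25 × 0.1414) = 3.677, power 95.5%. This matches the 95% in the synopsis.

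The normal approximation gives 97.9% and 95.7%. Swapping the SDs misses each stated figure by more than 2 points, so neither rounding nor a slip in one power value explains the difference. A one-sided test would give 97.9% at SD 1.25, but both texts specify two-sided.

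**Step 2: per-etiology power under equal enrollment (n = 50, 98 df, critical value 1.984).**
- SD 1.15: λ = 0.65 / (1.15 × 0.2) = 2.826, power 79.9%. This matches the stated 80%.
- SD 1.25: λ = 0.65 / (1.25 × 0.2) = 2.600, power 73.1%. This does not match.

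**Step 3: size of the gap.** The variance ratio is (1.25/1.15)² = 1.18, so the synopsis assumes 18% more variance. At SD 1.25, 95% power needs 98 per arm, so the planned 100 supports the synopsis figure. To reach 80% within an etiology at SD 1.25 takes about 60 per arm (59 gives 79.98%), against the 50 assumed.

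**Step 4: the permitted imbalance.** Take the 60% cap to refer to the 200 randomized subjects, and allocation to be 1:1 within each stratum. The extreme split is then 120 to 80, which is 60 and 40 per arm.

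| Etiology | n per arm | Power, SD 1.15 | Power, SD 1.25 |
|---|---|---|---|
| Either, equal enrollment | 50 | 79.9% | 73.1% |
| Larger, at the cap | 60 | 86.7% | 80.6% |
| Smaller, at the cap | 40 | 70.4% | 63.2% |

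**The case against.** The strongest reply is that nothing in the design depends on the discrepancy. Sample size, difference and test are identical in the two places, each stated power is correct for its own SD, and the primary comparison keeps at least 95% power. That is true, and it limits the point to the accuracy of what is stated.

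Second, the 73% contradicts no printed figure. The synopsis makes no per-etiology claim, and the 80% stands next to the SD on which it is correct. This is also fair: 73% is what follows if 1.25 is the chosen SD, not a second error. It still has to be stated, because on that choice the sentence in Section 11.1 would no longer be true.

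Third, the etiology analyses are optional, and the supplied text attaches no etiology-specific hypothesis or success criterion to them. The 80% is also expressly conditional on equal enrollment, so a cap that permits imbalance does not contradict it. Both points stand. The figures at the cap are a useful addition, and the finding does not depend on them.

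Finally, only the synopsis and Section 11 were available, so a source for either SD may exist elsewhere in the protocol. A missing justification is therefore not counted as a fault. A source elsewhere would not remove the conflict between the two values.

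The provision in Section 11.2 that lets a later SAP record changes in statistical methods does not help either. It concerns methods, and does not reconcile two planning SDs.

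**Conclusion.** The concern holds. The two sample-size statements are each internally correct but rest on incompatible SDs, and the text reviewed does not reconcile them. For the primary comparison the effect is small: 97.8% or 95.5% power at 100 per arm. The practical effect is on the per-etiology statement, which is 79.9% under one SD and 73.1% under the other, a loss of about 7 points, even with equal enrollment.

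The per-etiology figures assume that the 0.65-point difference applies within each etiology. The figures at the cap also assume that it is counted on the 200 randomized subjects, with 1:1 allocation within strata. Which SD is right cannot be decided from the documents. The correction should be made because a stated power and its SD are figures that readers rely on, but it does not call the design into question.

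**What to change.** Choose one SD, give its justification, and use it in both the synopsis and Section 11.1, with power figures to match:

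- **If SD 1.15:** overall power about 98%; per-etiology power about 80% at 50 per arm.
- **If SD 1.25:** overall power about 95%; per-etiology power about 73% at 50 per arm.

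Keep the equal-enrollment condition on the per-etiology figure. If the two SDs were meant for different quantities, say so and define each.

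As an optional addition, one clause could state that if enrollment reaches the 60% cap, the smaller etiology (40 per arm, counting the cap on the 200 randomized subjects and assuming 1:1 allocation within strata) has about 70% power at SD 1.15 or about 63% at SD 1.25.

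The cost is wording in two places. If SD 1.25 is kept, the stated figures become less favourable: 98% falls to 95% overall and 80% to 73% per etiology. Sample size and analysis stay as they are.

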11.2. Statistical Methods and Analysis Plan

This section describes the planned statistical analyses in general terms. A complete description of the methodology will be specified in a statistical analysis plan (SAP). Any changes in the statistical methods described in this protocol that occur prior to database lock will be documented in the SAP and will not require a protocol amendment.

11.2.1. General

Statistical analyses will be performed using two-sided tests.

Data will be summarized by treatment group (and by visit when applicable), with respect to demographic and baseline characteristics, efficacy variables, and safety variables.

Summary statistics will include the mean, N, standard deviation, median, minimum, and maximum values for continuous variables, and frequencies and percentages for categorical variables.

Continuous efficacy variables will be analyzed using a mixed-effect model for repeated measures (MMRM) and/or an analysis of covariance (ANCOVA) model. The models will be described in the SAP.

For the analyses of change from baseline, only subjects with a baseline and at least one (1) post-baseline measure will be included in the analysis. Unless otherwise specified, baseline is defined as the latest non-missing observation across all the visits in the screening phase, before the active study drug begins. Endpoint will be the latest non-missing observation across all the post-baseline visits in the evaluation phase.

Low enrolling sites will be pooled for analysis and the pooling algorithm will be determined prior to breaking the blind. The goal of pooling low enrolling sites is to have a sufficient number of subjects per treatment group within a site for the analysis models and for the evaluation of the treatment-by-site interaction for the primary endpoint. Unless otherwise specified, the pooled sites will only be used in the analyses where site is included. The actual sites rather than the pooled sites will be specified in data listings.

Categorical variables will be analyzed using the Cochran-Mantel-Haenszel (CMH) test blocking on sites, and Fisher's exact test will be used when site is not adjusted (mainly for safety assessment).

Details of the model and the analyses will be specified in the SAP. All statistical analyses will be performed using SAS®, Version 9.1.3 or higher.

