11.3. Efficacy Data Analysis

11.3.1. Primary Outcome and Methodology

The primary efficacy outcome measure will be change from baseline to Week 12 (Visit 8) in daily nausea severity score. A repeated measures analysis employing a restricted maximum likelihood (REML)-based, mixed-effects model approach (MMRM) will be used to analyze the primary efficacy outcome. The MMRM model will include the fixed, categorical effects of treatment group assignment, visit, treatment group-by-visit interaction and pooled site as well as the fixed, continuous covariates of baseline symptom score and the baseline symptom score-by-visit interaction. A detailed description of the MMRM model will be included in the SAP.

In addition to the MMRM model, an analysis of covariance (ANCOVA) model will also be applied. The last-observation-carried-forward (LOCF) will be used to impute any subsequent missing data. The model will have baseline as a covariate, and the fixed, categorical effects of treatment group assignment, pooled site. An observed cases (OC) analysis will also be performed.

As stated previously, any changes in the statistical methods that occur prior to database lock will be documented in the SAP and will not require a protocol amendment.

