11.3.2. Secondary Efficacy Analysis

The secondary efficacy outcomes include:

- -
- Other Gastroparesis Core Symptoms: vomiting, early satiety, post-prandial fullness, and upper abdominal pain;
- Gastroparesis Cardinal Symptom Index (GCSI, calculated out of PAGA-SYM)
- PAGA-SYM
- Global Assessment of Gastroparesis
- Patient Rated Change in Gastroparesis Symptoms
- PGI-C
- PAGA-QOL
- GTBS
- CGI-S

Continuous endpoints will be summarized and analyzed in a manner similar to the primary endpoint. Details of the analysis will be described in the SAP.

Categorical variables will be evaluated as described in the SAP. Time to event data will be analyzed using the Kaplan-Meier method, and the treatment group differences will be tested by the log-rank test. Details of the analysis will be described in the SAP.

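### Secondary outcomes analysed as categorical are tested by CMH on pooled sites, without baseline severity or etiology: a modest loss of efficiency, not of validity

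*SAP*

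**What the plan says.** SAP section 11.2.1 gives one test for categorical variables where site is adjusted for: "Categorical variables will be analyzed using the Cochran-Mantel-Haenszel (CMH) test blocking on sites". Fisher's exact test is for analyses without site, mainly safety. The preceding paragraph deals with small sites: "Low enrolling sites will be pooled for analysis and the pooling algorithm will be determined prior to breaking the blind", and "Unless otherwise specified, the pooled sites will only be used in the analyses where site is included". No minimum pool size is given.

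Section 11.3.1 treats the primary endpoint differently. Its MMRM has "fixed, continuous covariates of baseline symptom score and the baseline symptom score-by-visit interaction" as well as pooled site, and its ANCOVA has baseline and pooled site. Section 11.3.2 analyses continuous secondary endpoints in much the same way as the primary. For the others it says only "Categorical variables will be evaluated as described in the SAP", meaning a fuller SAP that is not among the documents.

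The protocol synopsis shows what baseline information exists. Group 1 entry requires at least 24 screening diary entries and sets a floor of 2.5, on the 0-5 scale, for "Average daily diary nausea severity". Under Overall Design it says "Randomization will be stratified by disease etiology (idiopathic or diabetic"); neither site nor severity is named as a stratum. The synopsis plans "Approximately 50 centers in the United States" and 200 randomized subjects.

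**The concern.** A subject's rating after 12 weeks probably depends in part on how ill the subject was at entry. A test that ignores baseline leaves that variation in the error term. The plan removes it for continuous outcomes but not for categorical ones, and gives no reason for the difference. Etiology was important enough to stratify on, yet it does not enter the categorical test either. (The primary models do not list etiology, so the contrast with them concerns baseline only.)

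At stake is power on any secondary outcome handled as categorical. The global and clinician ratings are natural candidates, and they help a reader judge whether a change in diary nausea matters to patients. The primary endpoint is not affected.

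**Working it through.** **The plan's own figures.** The documents state no power for any categorical endpoint. Their continuous figures reproduce. Power = Φ(δ / (σ√(2/n)) − 1.96).
- SAP 11.1, 100 per arm, δ = 0.65, σ = 1.15: Φ(3.997 − 1.96) = 97.9%, against about 98% stated.
- SAP 11.1, 50 per arm (one etiology): Φ(2.826 − 1.96) = 80.7%, against about 80% stated.

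**Step 1: what blocking on site costs.** Allocation is not stratified by site, so chance imbalance within K blocks loses an expected share (K − 1)/199 of the information. As an anchor, assume responder rates of 30% and 50% (not in the documents) with 100 per arm. Power is Φ((0.2 − 1.96√(2×0.4×0.6/100)) / √((0.21 + 0.25)/100)) = Φ(0.947) = 82.8%, a noncentrality of 0.947 + 1.96 = 2.907.
- 10 pools: 9/199 = 4.5% lost; 2.907 × √0.955 = 2.840; power 81.1%, a loss of about 2 points.
- 20 pools: 19/199 = 9.5% lost; 2.764; power 78.9%, a loss of about 4 points.
- 50 unpooled sites: 49/199 = 24.6% lost; 2.524; power 71.3%, a loss of about 11 points.

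Simulation of the same binary endpoint (200 subjects, 50 equal or uneven sites, site SD 0 or 0.5 on the logit scale, 3,000 runs per scenario) gave these powers in %:

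| Severity slope (log-odds per SD) | No stratification | CMH, 50 raw sites | CMH, 20 pools | CMH, 10 pools | Logistic with severity |
|---|---|---|---|---|---|
| 0 | 81.3-83.5 | 71.2-77.1 | 77.7-80.6 | 79.5-82.1 | 81.3-83.1 |
| 0.5 | 83.3-84.6 | 72.3-77.0 | 79.4-80.6 | 81.0-82.2 | 84.7-85.8 |
| 1.0 | 82.3-83.6 | 70.1-75.3 | 78.4-80.0 | 80.8-81.7 | 87.7-88.7 |

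Losses against no stratification are about 1-2 points with 10 pools and 3-5 with 20, in line with the formula. The logistic model beats CMH on 10 pools by 3-4 points at slope 0.5 and 6-8 at slope 1.0. Of that, 1-2 points come from dropping the site blocks, as the first row shows.

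**Step 2: what baseline adds on an ordered rating.** To isolate baseline, keep the pools and add it. Assumed: 7 categories, 200 subjects, 50 uneven sites pooled to 10, latent effect 0.4 SD, site SD 0 or 0.3.
- CMH on 10 pools: 71-75% power.
- Score model with the same pools plus baseline: 77-78% at correlation 0.3; 81-86% at 0.5.
- At correlation 0, a score model with baseline gives 73-76%, against 73-75% for CMH on 10 pools: no gain and no penalty.

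With 10 or 20 pools, the gain is about 3-4 points at 0.3 and about 10 at 0.5. A hand check treats the rating as a continuous score, so that adjustment divides the noncentrality by √(1 − r²). Start from 73%, the middle of 71-75%: noncentrality 0.613 + 1.96 = 2.573.
- r = 0.3: 2.573/√0.91 = 2.697; power Φ(0.737) = 76.9%, a gain of 3.9 points.
- r = 0.5: 2.573/√0.75 = 2.971; power Φ(1.011) = 84.4%, a gain of 11.4 points, slightly above the simulated figure.

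**Step 3: validity.** With no treatment effect, rejection rates were 4.5-5.7% in the binary simulation and 4.4-5.8% in the ordinal one, across all methods.

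The contribution of etiology was not simulated; the documents give nothing on how it relates to these ratings.

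**The case against.** A reader might infer from about 50 centers and 200 subjects, roughly 4 per center, that the test blocks on tiny sites and throws many of them away. The documents do not support this. The paragraph before the CMH sentence pools low-enrolling sites and applies the pools wherever site is included, and this test is such an analysis. The 11-point loss belongs to raw sites, which the text does not plan. What is left is that the CMH sentence says sites where the MMRM says pooled site, and that no minimum pool size is given.

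A reader might also infer that the global and clinician ratings will certainly get the weaker method. Section 11.3.2 does not label any listed outcome as categorical. A rating scored as continuous would follow the primary method, with baseline adjustment where a baseline exists.

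Three further objections have weight. Section 11.2 describes itself as general and defers detail; but it states a method, and that method will carry forward unless changed. CMH needs no proportional-odds assumption, which is a fair reason to like it and the reason to keep it as a check. Finally, the size of the gain rests on assumed inputs. Some ratings are of change and so have no baseline of their own. For these the covariate would be screening nausea, a different instrument whose range is narrowed by the 2.5 floor.

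**Conclusion.** The point holds as one of efficiency. The stated test for categorical variables leaves out a baseline that the trial collects and already uses for its continuous outcomes, and leaves out the randomization stratum. Type I error is not at risk.

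The gain from adding baseline is about 3-4 power points at a correlation of 0.3, about 10 at 0.5 and none at 0, for a 7-category rating with a latent effect of 0.4 SD and 10 to 20 pools. All of these inputs are assumptions, and the documents do not allow one value to be chosen within that range. Most of the gain comes from baseline rather than from removing site blocks. It reaches only those secondary outcomes that end up being analysed as categorical.

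**What to change.** In SAP section 11.2.1, make the main analysis of categorical efficacy outcomes a proportional-odds model, or logistic regression for binary outcomes, with treatment, etiology and baseline severity. Baseline severity is the scale's own baseline where it has one, and otherwise the screening-average nausea score. Keep CMH as a sensitivity analysis, and let its sentence say pooled sites, as the MMRM does. In section 11.3.2, point to this model and list the outcomes it applies to.

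The cost is SAP wording. No new data are needed, and section 11.2 lets methods change before database lock without a protocol amendment. The one real downside is the proportional-odds assumption, for which the retained CMH test is the check. If baseline turns out to be unrelated to the rating, the simulations show no penalty.
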